13.8 Adverse Event Reporting

All AEs should be reported on the AE form within the CRF. An adverse reaction (AR) is an AE which is related to the administration of the study drug. All ARs must be reported on the AE form within the CRF.

An unexpected adverse reaction (UAR) is an AE which is related to the administration of the study drug and that is unexpected, in that it has not been previously reported in the current IB. All UARs must be reported on the AE form within the CRF.

These events will be included as part of the safety analysis for the trial and do not require expedited reporting to the CTU.

13.9 Serious Adverse Event Reporting

A SAE is defined as an AE that fulfils one or more of the criteria for seriousness outlined in Table 3. SAEs that are related to the administration of the study drug are SARs. SUSARs are SAEs that are considered to be caused by the study drug and are unexpected i.e. their nature or severity is not consistent with the IB. All SAEs, SARs and SUSARs must be reported to the CTU.

If a SAE occurs, reporting will follow the regulatory requirements as appropriate and all SUSARs will be the subject of expedited reporting. SAEs will be evaluated by the PI for causality (i.e. their relationship to study drug) and expectedness (if related). SAEs will be reported using the SAE Form and must be reported to the CTU within 24 hours of becoming aware of the event. The PI should not wait until all information about the event is available before notifying the CTU of the SAE. The CTU will acknowledge receipt of the SAE Form within two working days by email to the site. Information not available at the time of the initial report must be documented on a follow up SAE Form. Follow up information should be sought and submitted as it becomes available. The follow up information should describe whether the event has resolved or persists, if and how it was treated and whether the patient continues on the study or has been withdrawn from treatment.

The CTU is responsible for reporting SAEs to the Sponsor, ethics committee, and MHRA within the required timelines as per the regulatory requirements. A fatal or life threatening SUSAR must be reported within 7 days after the CTU has first knowledge of such an event. Relevant follow up information will be sought and communicated within an additional 8 days. All other SUSARs will be reported to the relevant competent authorities and research ethics committees within 15 days after the knowledge of such an event.

13.10 Recording and Reporting of Urgent Safety Measures

In the event that the CI becomes aware of information that necessitates an immediate change in study procedure, to protect clinical trial subjects from any immediate hazard to their health and safety the CI should phone the Clinical Trial Unit at the MHRA and discuss the issue with a medical assessor immediately once an urgent safety measure has been taken at site.

Following this initial telephone call the CI must immediately report to the Sponsor who will inform MHRA and REC in writing within 3 days of the incident. Written notification in the form of a substantial amendment is also required.

The CTU will assist the CI to ensure adherence to reporting requirements to REC and MHRA and must be kept fully informed of any changes implemented or required.

13.11 Pregnancy

13.11.1 Contraceptive Advice

While ARA 290 has not been shown to adversely affect pregnancy or harm the fetus in two animal studies, it is an investigational drug and therefore pregnant or breast feeding women will be excluded from the study. A pregnancy test will be performed in every woman of child-bearing age before she is included into the study. All non-pregnant women of child-bearing age will be instructed at the beginning of the study, before receiving the study drug, that it is essential that they use effective contraception to prevent pregnancy e.g. oral contraceptive and condom, intra-uterine device (IUD) and condom, diaphragm with spermicide and condom. This contraceptive should be continued for at least 30 days post administration of the final dose of the study drug. Women who refuse to take effective contraception will not be permitted to enter the study, and women who stop using effective contraception during the course of the study will be discontinued from study participation.

Male study participants will be advised that they should not father a child during this study and for a safety period of 30 days after final treatment. To ensure this, male participants will be advised that they or their partner must use reliable forms of contraceptive during the trial and for 30 days afterwards, e.g. oral contraceptive and condom, intra-uterine device (IUD) and condom, diaphragm with spermicide and condom.

13.11.2 Pregnancy Reporting

Women who become pregnant during the study should stop ARA 290 immediately and inform the PI. Male study participants should inform the PI if their partner becomes pregnant while he is in the study. Pregnancy is not considered an AE or SAE, however an abnormal outcome would be. Therefore the PI or designee must collect pregnancy information for female participants, and for females who become pregnant while their partners are participating in the trial. Consent should be obtained to follow up the pregnancy from the female partners of male participants.

The pregnancy reporting period for the trial is from the commencement of the study drug until 30 days post admin of the final dose of study drug. The PI or designee should complete and submit the Pregnancy Reporting Form to the CTU by email within 14 days of being made aware of the pregnancy. The CTU will acknowledge receipt of the Pregnancy Reporting Form within two working days by email to the site.

Any pregnancy that occurs in a participant or participant's partner during the trial should be followed to outcome. Follow up/outcome information should be provided to the CTU as soon as it becomes available. Araim Pharmaceuticals, Inc. may also request their consent to collect confidential information about their health and that of the baby.

An unwillingness to undertake adequate precautions to prevent pregnancy for the duration of the trial is an exclusion criteria for this study.

14 DATA MONITORING

14.1 Data Access

Prior to commencement of the study, the PI will give permission for trial related monitoring, audits, ethics committee review and regulatory inspections, by providing direct access to source data and trial related documentation. Consent from patients for direct access to data will also be obtained. The patients' confidentiality will be maintained and will not be made publicly available to the extent permitted by the applicable laws and regulations.

14.2 Monitoring Arrangements

The CTU will be responsible for trial monitoring. On-site monitoring visits will be conducted in accordance with the trial monitoring plan. On-site monitoring will be an on-going activity from the time of initiation until trial close-out and will comply with the principles of Good Clinical Practice (GCP) and European Union (EU) directive 2001/20/EC. The frequency and type of monitoring will be detailed in the monitoring plan and agreed by the trial Sponsor.

Before the trial starts at a participating site, an initiation visit will take place to ensure that all relevant essential documents and trial supplies are in place and that site staff are fully aware of the trial protocol and procedures. On-site monitoring visits during the trial will check the accuracy of entries on CRF's against the source documents, the adherence to the protocol, procedures and GCP, and the progress of patient recruitment and follow up. Monitoring will also ensure that the trial drug is being stored, dispensed and accounted for according to specifications.

The PI or designee should ensure that access to all trial related documents including source documents (to confirm their consistency with CRF entries) are available during monitoring visits. The extent of source data verification (SDV) will be documented in the monitoring plan.

The site close out procedure will commence following the completion of the 12 week follow up period of the final patient (16 weeks in the event that the patient retina is dry at the 12 week visit).

15. TRIAL COMMITTEES

15.1 Trial Management Arrangements

The CI will have overall responsibility for the conduct of the study. As this study is a single site study, the CI will also act as PI. The CTU will undertake trial management including all clinical applications (MHRA, ethics. research governance), management, trial and IMP pharmacovigilance, site initiation/training, monitoring, analysis and reporting. The Trial Manager will be responsible on a day to day basis for overseeing and co-ordinating the work of the multi-disciplinary trial team, and will be the main contact between the trial team (section 2) and other parties involved. The CTU will assist and facilitate in the setting up and co-ordination of the trial committees including the Trial Management Group (TMG) and Data Monitoring and Ethics Committee (DMEC).

15.2 Trial Management Group (TMG)

A Trial Management Group (TMG) will be established and Chaired by the CI. The TMG will have representation on it from the CTU and other investigators/collaborators who are involved in the study and provide trial specific expertise (e.g. trial statistician). This group will have responsibility for the day to day operational management of the trial, and regular meetings of the TMG will be held to discuss and monitor progress. The discussions of the TMG will be formally minuted and a record kept in the TMF.

A TMG Charter will be drawn up to detail the terms of reference of the TMG including roles and responsibilities. A Trial Steering Committee (TSC) will not be established for the trial and therefore the TMG will oversee the progress of the trial in terms of its organisation and accrual with the aim of steering it towards its overall objectives and will report to the Sponsor/Funder.

15.3 Data Monitoring and Ethics Committee (DMEC)

A DMEC will be appointed comprised of one diabetologist ([name]), two ophthalmologists with expertise on DR and DMO ([name] and [name]), and a Statistician ([name]) who is experienced in the analysis of clinical trials and will act as Chair for the DMEC. These members will be independent of the trial. A DMEC Charter will be drawn up to detail the terms of reference of the DMEC including roles and responsibilities. The DMEC's responsibility is to safeguard the interests of the trial participants, in particular with regard to safety, and to protect the validity and credibility of the trial. DMEC meetings will be formally minuted.

The inaugural meeting of the DMEC will take place prior to recruitment commencing. After recruitment commences the DMEC will review safety data at approximate 4 week intervals (with the first review commencing approximately 8 weeks after the first patient is recruited). The Chair of the DMEC will decide if these reviews raise any issues or concerns which require the DMEC to meet to discuss further. In addition, approximately every 3 months, the DMEC will review a full report on trial data (including outcome data, recruitment, pharmacovigilance and protocol deviations).

The DMEC will advise if in their view, the data arising from the study has provided 'proof beyond reasonable doubt' that for all, or some, the treatment should not be continued and standard treatment should be provided. Following a report from the DMEC, the CI will decide in consultation with the Sponsor what actions, if any, are required.

Membership of the DMEC will include:

[name], (Chair), Associate Professor, Deputy Director of SITU, Centre for Statistics in Medicine, Nuffield Department of Orthopaedics, Rheumatology & Muscoskeletal Sciences, University of Oxford, Botnar Research Centre, Nuffield Orthopaedic Centre, [name]

[name], Chair of Diabetes and Translational Research, Institute of Clinical Sciences; Block A, Queen's University Belfast, [name]

[name], Honorary Clinical Senior Lecturer, Institute of Genetic Medicine, Newcastle University

[name], Consultant Ophthalmologist, Moorfield Eye Hospital, [name]

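### In the protocol and SAP, the only standard for DMEC advice against continuing treatment is near-certain proof, which fits its safety role poorly, and Protocol 13.9 gives it no prompt sight of SAEs

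*Protocol*

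**What the plan says.** Protocol 15.3 gives the DMEC the duty "to safeguard the interests of the trial participants, in particular with regard to safety". On advice against continuing, the same section says: "The DMEC will advise if in their view, the data arising from the study has provided 'proof beyond reasonable doubt" that treatment should cease, for all patients or some, in favour of standard care. SAP 8.2 repeats both statements.

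On what the committee sees and when, Protocol 15.3 says that "the DMEC will review safety data at approximate 4 week intervals", "with the first review commencing approximately 8 weeks after the first patient is recruited". A fuller report, including pharmacovigilance, follows about every 3 months. Meetings depend on those reviews: "The Chair of the DMEC will decide if these reviews raise any issues or concerns which require the DMEC to meet to discuss further". After that, "Following a report from the DMEC, the CI will decide in consultation with the Sponsor what actions, if any, are required". A Charter is promised but is not among the documents.

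On serious events, Protocol 13.9 says that SAEs "must be reported to the CTU within 24 hours of becoming aware of the event". Onward, "The CTU is responsible for reporting SAEs to the Sponsor, ethics committee, and MHRA". SUSARs have limits of 7 days (fatal or life-threatening) and 15 days (others). The DMEC is not mentioned in 13.9.

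**The concern.** A safety committee normally advises on the balance of risk and benefit. A proof standard asks for much firmer evidence, and this trial is poorly placed to supply it: 10 patients, no control arm, descriptive analysis. It is also the first study of the drug to run to 84 days, and participants take it in place of standard anti-VEGF treatment (Protocol 9.6).

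The DMEC's position makes its wording matter. The CI is also the PI (Protocol 15.1) and chairs the Trial Management Group, and there is no Trial Steering Committee (15.2). The DMEC is the only trial committee described as independent of the trial. If its members took the wording at face value, they might hold back advice that a judgement of risk and benefit would already support. If they first learn of a serious event at a scheduled review, the advice comes later still.

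**Working it through.** Neither document attaches a number to the DMEC standard or derives the sample size of 10, so there is no stated figure to reproduce. The check compares sections and works out the review intervals.

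**Step 1. Is there any other criterion for this advice?**

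| Place | What it governs | Criterion for DMEC advice? |
|---|---|---|
| Protocol 15.3, SAP 8.2 | Advice that treatment should not continue | Yes, the proof standard |
| Protocol 15.3, Chair's decision | Whether the committee meets | No |
| Protocol 5.4, SAP 2.4 | Sponsor stopping the trial, for example on DMEC recommendation | None given |
| Protocol 9.6 | Stopping drug in one patient after a 10-letter loss | No, a patient-level rule |

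Only the first row sets a standard for the advice.

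**Step 2. Does the standard suit the trial?** The inputs are 10 patients (Protocol 12.1), one open-label regimen (5.1), descriptive statistics (12.3), and 84 days of dosing against 28 in most earlier studies (3.3). With no control arm, the trial does not estimate how often an event would occur without the drug. An excess of harm would therefore have to be judged, and could rarely be proved in any formal sense. That supports calling it a poor fit. It is a judgement, not a calculated result.

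**Step 3. How long might the DMEC wait to see an SAE?** Assume that it sees events only at the scheduled reviews and that these run to time.

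- Between reviews: 4 weeks × 7 = about 28 days at most.
- Before the first review: 8 weeks × 7 = about 56 days at most, for an event just after the first patient starts.
- First patient's exposure at the first review, if dosing starts at recruitment: about day 56 of 84. That is 56 / 28 = 2 times the duration used in most previous studies.

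**Step 4. Who could hear first?** The SUSAR limits of 7 and 15 days are both shorter than 28 days, so the MHRA and research ethics committee could learn of a SUSAR before the DMEC does. For other SAEs, 13.9 refers only to required timelines and gives no number of days, so no order can be claimed. The ethics committee in 13.9 is read as the REC, not the DMEC.

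**The case against.** The strongest reply is that the Charter is the usual home for advisory criteria and SAE copying, and it has not been seen. That stands, and it limits the point to the two documents supplied.

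Next, 13.9 deals with reporting from the site to the CTU and regulators, while 15.3 governs what the DMEC receives. The CTU handles pharmacovigilance and also supports the DMEC (Protocol 15.1), so nothing prevents earlier notice. This is fair, but nothing in either section requires it.

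There are also real safeguards outside the committee:

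- The REC, MHRA or sponsor can stop the trial (5.4).
- The patient or PI can stop the drug (8.4), and a 10-letter loss requires it (9.6).
- Patients are observed for one hour after the first dose (9.5) and telephoned at 2 weeks (10.10), and adverse events are checked at weeks 2, 4 and 8 (Table 2).
- Urgent safety measures are available (13.10).
- Animal dosing for up to 6 months in rats and 9 months in rabbits showed no adverse effects (3.3).

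These lower the practical risk. They do not make the committee's own standard suitable.

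Three stronger readings are tempting, and the documents support none of them.

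- **That the DMEC may not advise stopping without proof.** The sentence says when it will advise, not that it may advise only then, and it leaves the matter to the members' view.
- **That the DMEC would never see SAEs.** The 4-weekly reviews and 3-monthly reports provide for this. Only promptness is in question.
- **That the standard amounts to a count of affected patients.** Treated as a one-sided binomial test at 0.01 or 0.001 against a background of 5% to 20%, it would need about 4 to 7 of 10. At a background of 1% to 2% it would need 2 to 3, and one clearly drug-caused event might be enough. The backgrounds and the test levels are all assumed, and the plan asks for no such test. The counts are no measure of harm.

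**Conclusion.** The point holds in a limited form. Within the protocol and SAP, the only standard for DMEC advice against continuing is one of near-certain proof, and it sits badly beside a safety duty in a small, uncontrolled pilot with extended dosing. The protocol also provides no prompt notice of SAEs to the DMEC.

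The size is the review intervals and nothing more: up to about 28 days between reviews, and about 56 days before the first. This assumes that the Charter adds nothing, that no one informs the committee informally, and that reviews keep to schedule. Nothing shows that advice would in fact be delayed. This is an inexpensive improvement, not a flaw that undermines the trial.

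**What to change.** 1. In Protocol 15.3, replace the standard with: *The DMEC will advise if, in its judgement, the balance of risk and benefit no longer supports continuing treatment for all or some participants.* Align SAP 8.2.
2. In Protocol 13.9, add: *The CTU will copy every SAE and SUSAR to the DMEC Chair and clinical members within two working days of receipt. For any drug-related SAE or SUSAR the Chair, with a clinical member, will consider whether to call an ad hoc review.*

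The fixed deadline matters because 13.9 sets no number of days for SAEs that are not SUSARs. Two working days is already the CTU's limit for acknowledging an SAE form. Clinical members are included because the Chair is the statistician. The addition prompts consideration only: it sets no count rule, pauses no dosing and leaves the review schedule alone.

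SAP 6 records that no patient needed the 16-week visit, which implies that the week-12 visits were complete when that text was written. The SAP edit is therefore for consistency, and the protocol is where the change would act.

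The cost is a few sentences, one copied email per SAE that the CTU already holds, and an occasional DMEC call about an event later judged unrelated. After approval, the change may need regulatory or ethics agreement before use (Protocol 16.9). If the Charter already contains both provisions, a cross-reference to it and the wording change in 15.3 would be enough.

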16. REGULATIONS, ETHICS AND GOVERNANCE

The trial will comply with the principles of GCP, the requirements and standards set out by the EU Directive 2001/20/EC and the applicable regulatory requirements in the UK, the Medicines for Human Use (Clinical Trials) Regulations 2004 and subsequent amendments and the Research Governance Framework.

16.1 Sponsorship

The Belfast Health and Social Care Trust (BHSCT) will act as Sponsor for the study and the CI will take overall responsibility for the conduct of the trial. Separate agreements will be put in place between the Sponsor, CI and each organisation who will undertake Sponsor delegated duties in relation to the management of the study.

16.2 Funding

This study is funded by ARAIM PHARMACEUTICALS, INC. [name]. Funding provided by Araim Pharmaceuticals covers the costs for staff based at the Clinical Trials Unit (CTU) the trial co-ordinating centre for the study, staff costs incurred by participating sites (including Research Nurse, Photographer and Optometrists time), study consumables and pharmacy costs. Araim Pharmaceuticals Inc. will also supply the investigational medicinal product (IMP) for the study.

16.3 Indemnity

The BHSCT will provide indemnity for any negligent harm caused to patients by the design of the research protocol through the Clinical Negligence Fund in Northern Ireland.

16.4 Contributorship

The CI conceived and designed the study protocol with input from Araim Pharmaceuticals. The CI is also the grant holder and will oversee the management and conduct of the study.

The Trial Statistician and Trial Manager from the NICTU contributed to the development of the protocol and study design. The Trial Statistician provided statistical advice and will oversee the analysis. The BHSCT Pharmacist contributed to the development of the protocol and provided pharmaceutical advice.

16.5 Competing Interests

The research costs including the cost of the intervention were funded by Araim Pharmaceuticals. The CI and members of the TMG have no financial or non-financial competing interests and the members of the DMEC will be asked to confirm that they have no conflict of interest. In the event that a DMEC member reports a conflict of interest, advice will be sought from the Sponsor.

16.6 Regulatory and Ethical Approvals

The trial will be conducted in accordance with the ethical principles that have their origin in the Declaration of Helsinki. The protocol will be approved by a Research Ethics Committee.

A Clinical Trial Authorisation (CTA) will be obtained from the Medicines for Human Use Regulatory Authority (MHRA) before the start of the trial.

16.7 Good Clinical Practice

The trial will be carried out in accordance with the principles of the International Conference on Harmonisation Good Clinical Practice (ICH-GCP) guidelines (www.ich.org). All members of the trial team will be required to have completed GCP training.

16.8 Protocol Compliance

A protocol deviation is defined as an incident which deviates from the normal expectation of a particular part of the trial process. Any deviations from the protocol will be fully documented on the protocol deviation form in the CRF.

A serious breach is defined as a deviation from the trial protocol or GCP which is likely to effect to a significant degree:

- (a) the safety or physical or mental integrity of the subjects of the trial; or
- (b) the scientific value of the trial

The PI or designee is responsible for ensuring that serious breaches are reported directly to the Sponsor within one working day of becoming aware of the breach.

